3.6.3. Rationale for Dose

The proposed doses of GSK2849330 are based on available preclinical biology, toxicology, and PK data as well as predicted PK and pharmacologic response information for humans and are consistent with International Conference on Harmonisation (ICH) guidelines for FTIH oncology studies. Guidance for first in human studies with biologics, expert viewpoints on FTIH oncology studies with molecularly targeted therapeutics [LeTourneau, 2010], and recent preliminary safety data reported for anti-HER3 mAbs were also considered when proposing doses of GSK2849330 (refer to Section 1.3 for details).

In nonclinical GLP toxicology studies, GSK2849330 was given as a once-weekly IV infusion to rats and cynomolgus monkeys for up to 4 weeks with up to 6-week off-treatment period. In the rat, there were no adverse findings up to and including the top dose studied (500 mg/kg/wk). In monkeys, abnormal fecal consistency was observed in male animals at the top dose studied (300 mg/kg/wk) and in female animals at \geq 30 mg/kg/wk. In a single monkey in the top dose group (300 mg/kg/wk), mild cecal and colonic ulcers were observed at terminal necropsy. The NOAEL, STD10 (severely toxic dose in 10% of animals [rat], and HNSTD (highest non-severely toxic dose [cynomolgus monkey]), and HED (human equivalent dose) corresponding to the STD10 or HNSTD are summarized in Table 2.

Table 2 NOAEL, NSTD10 (rat), and HNSTD (primate) from GLP Toxicology Studies and HED Predictions^a

	NOAEL Dose (mg/kg/wk)	NOAEL AUC (0-168 h) (mg*hr/mL)	STD10 or HNSTD Dose (mg/kg/wk)	Human Equivalent Dose (mg/kg/wk)
Rat	500	573	\geq 500	\geq 81
Cyno	30	102	\geq 300	\geq 97

AUC = area under the concentration-time curve; Cyno = cynomolgus monkey; HED = human equiv. dose
HNSTD = highest non-severely toxic dose; NOAEL = no observed adverse effect level; STD10 = severely toxic dose in 10% of animals.

a. HED corresponding to the STD10 (rat) or HNSTD (Cyno) as calculated scaled using scaling factor described in the FDA FTIH guidance

Refer to Section 1.2 and the IB [GlaxoSmithKline Document number 2013N168399_01] for additional information on the preclinical biology and toxicology studies.

Starting Dose

The proposed starting dose is 1.4 mg/kg, administered once-weekly. According to ICHS9 guidance, calculating a starting dose based on HNSTD/6 in the most relevant species (cynomolgous monkey) yields a starting dose of \sim 16 mg/kg/wk. We selected a more conservative starting dose of 1.4 mg/kg/wk, slightly above the MABEL calculated from tumor xenograft studies, which in turn suggests that clinical activity may be observed at dose levels of 1.2 mg/kg and higher.

Table 3 Dose Levels

Cohort	Dose	N Dose Escalation Cohorts	N PK-PD Cohorts
1	1.4 mg/kg weekly	1 (minimum)	up to 3
2	3 mg/kg every 2 weeks	3 (minimum)	up to 3
3	10 mg/kg every 2 weeks	3 (minimum)	up to 3
4	30 mg/kg every 2 weeks	3 (minimum)	up to 3
5	30 mg/kg weekly (optional change to every 2 weeks after 24 weeks of treatment)	3 (minimum)	up to 3
Additional optional cohorts may be enrolled at different dose levels and intensities			

Maximum Proposed Dose

The maximum proposed dose of 30 mg/kg for weekly, bi-weekly or every three week dosing was selected based on PK-PD extrapolations which predict target engagement > 90% and tumor saturation should be achieved at or below this dose, and based on practical considerations (e.g., drug product supply and production capacity) Emerging PK, safety and tolerability data may cause the proposed maximum dose to be adjusted downward (see Section 3.3 for details of the N-CRM model assessment of safety data).

Dose Escalation

The proposed dose escalation scheme is based on a half-log step size, with the exception of the 30 mg/kg/wk dose and the nominal doses shown in Table 3 represent the maximum dose which may be selected. The study team, in discussion with the investigator(s), may select other doses or alternative schedules besides those shown, based on emerging safety, tolerability, PK and/or PD data.

Dosing Interval

The predicted half-life for GSK2849330 after the first dose is ~7 days and increases to ~10 to 14 days after repeated dosing and is expected to support dosing frequency from weekly to every three weeks. However, at lower doses, including the proposed starting dose, the contribution of target mediated clearance may yield a half-life somewhat shorter than projected for higher dose levels. With this consideration, the initial dosing frequency for the first subject will be once-weekly. PK data will be evaluated from the first week of dosing for the first subject, so that adjustments in the dosing interval can be made if appropriate (see the Time and Events Tables Section 7.1 and Section 7.4 for the specific PK assessment schedule for the first subject).

If the half-life appears to be generally in line with expectations, the dosing interval for higher dose cohorts is anticipated to be every week or every 2 weeks. A general guideline is shown in Table 4. Additional schedules may be explored based on safety, tolerability, PK and PD.

Table 4 Dosing Interval Guidance

Observed half-life	Likely dose interval*
<3 days	Once-weekly
4-8 days	Every week or every 2weeks
> 9 days	Every 3 weeks

*Final selection of dose interval for cohorts will take into consideration the half-life together with safety, tolerability, PK and available PD data.

It is recognized that increasing the dose can allow for extension of the dosing interval with equivalent safety and efficacy, assuming that 1) toxicity is not limited by C_{max} and 2) efficacy is related to overall exposure (AUC) or time above a given concentration. Both assumptions appear reasonable for GSK2849330 based on 1) preclinical safety data and 2) preclinical efficacy data and knowledge of the mechanism of action. Based on human PK predictions from cynomolgus monkey data, a dose of 2.9 mg/kg every 3 weeks IV may provide the same exposure in 3 weeks as 3 doses of 1.2mg/kg every week IV at steady state. Using these principles, it is anticipated that the dosing schedule may be lengthened as appropriate based on accrual of PK and/or PD information.

Additional context for the proposed doses are provided in the following sections.

Human Pharmacokinetic Extrapolation

Preliminary population PK parameters based on nominal dose and PK sample time as of September 2014 are listed in [Table 6](#) below for dose-escalation cohorts at 1.4 mg/kg (n=1), 3 mg/kg (n=2) or, 10 mg/kg (n=2). The data are modelled according to a two compartment PK model with peripheral Target Mediated Drug Disposition. The value of KM (concentration at half maximal saturation of peripheral target mediated drug disposition) is based on Biacore *in vitro* binding data together with an assumed 4/h rate of internalization and degradation based on semi-quantitative *in vitro* pulse chase experiment. One subject was excluded from the 3 mg/kg cohort because the dose was delayed; and another subject was excluded from the 10 mg/kg cohort because the infusion was terminated early so the total dose of GSK849330 administered was uncertain.

Table 6 Preliminary Population PK Parameters

Parameter	Unit	Estimate	%RSE	%CV
CL	mL/h	11.4	39.1	31.3
V1	mL	2830	6.64	
VM	µg/h	198	40.6	
KM	µg/mL	0.513		
Q	mL/h	79.0	19.1	
V2	mL	3420	13.7	
D1	h	1		
SG1 (proportional)		0.0626	62.9	

The compartmental and non-compartmental model parameters suggest a catabolic half-life of $(V1/CL) \times \ln(2) = 172$ hours.

Predicted Effective Dose

The potential therapeutic dose range for GSK2849330 in humans was derived using available preclinical *in vitro* and *in vivo* PK and efficacy data. In addition, data from mouse *in vivo* CHL-1 xenograft efficacy studies were evaluated to predict the potential minimum clinically efficacious dose. PK/PD modeling of CHL-1 xenograft data in SCID mice suggests that anti-tumor efficacy (based on tumor growth curves) may be achieved with systemic plasma trough concentrations of GSK2849330 maintained at ≥ 20 µg/mL. The predicted human equivalent dose to achieve a similar trough concentration in 90% of the population is approximately 1.4-3 mg/kg/wk. This dose is also in line with that projected, based on *in vitro* potency data, to engage HER3 and inhibit signaling (approximately 0.9 to 5.6 mg/kg). It is anticipated that optimal anti-tumor activity will require full target engagement and that ADCC and CDC enhancements may further increase the anti-tumor activity of GSK2849330. However, it is also recognized that saturation of target throughout the tumor in the clinical setting may require doses higher than those projected based on preclinical extrapolations, due to factors in the tumor microenvironment such as vascular perfusion heterogeneity which may limit mAb intra-tumoral distribution. Recognizing these factors, the top proposed dose for evaluation is 30 mg/kg, a dose which is also viewed as the highest dose feasible based on practical considerations.

A loading dose scenario is predicted to maintain an accumulated steady state trough concentration if the dosing interval is less than or equal to the elimination half-life. Accordingly, a 30 mg/kg weekly IV dose cohort has been added to the dose escalation portion of the study.

3.6.4. Rationale for Endpoints

The safety endpoints for all parts of the study (as described in Section 2.1 and Section 2.2) are designed to maximize subject safety, to allow for the identification and monitoring of emerging safety signals, and to allow for the identification of DLTs for determination of a MTD and/or recommended dose for further exploration.

Efficacy endpoints (as described in Section 2.1 and Section 2.2) will be collected to evaluate preliminary evidence of clinical benefit from treatment with GSK2849330.

Non-compartmental PK parameter values for GSK2849330 following IV administration, including area under the concentration-time curve from time zero (pre-dose) to last time of quantifiable concentration within a subject across all treatments [AUC(0-t)], Area under the concentration-time curve over the dosing interval [AUC(0- τ)], C_{max} and time of occurrence of C_{max} (t_{max}) and mean residence time (MRT) of GSK2849330 together with population compartmental PK parameters including clearance (CL), systemic volume of distribution (V), distributional clearance (Q), maximal rate (V_m), and concentration at half maximal rate (K_m) according to a Michaelis-Menten approximation of systemic target mediated clearance [Gibiansky, 2008], were selected to characterize the PK activity of GSK2849330.

Tumor, skin, and circulating biomarkers were selected based on the mechanism of action of GSK2849330, preclinical evidence in addition to clinical evidence reported in agents of the same class and in those affecting similar pathways. The objective is to characterize the PD effect of GSK2849330 and to obtain preliminary data on the relationship between HER3 expression levels (e.g., IHC 2+ and 3+), NRG1 expression, other potential predictive biomarkers including expression of other RTKs, mutations, immune associated markers, and efficacy outcome.

3.7. Study Treatment

3.7.1. Treatment Assignment

- Subjects will be identified by a unique subject number that will remain consistent for the duration of the study.
- Upon completion of all the required screening assessments, eligible subjects will be registered into RAMOS (Registration and Medication Ordering System), the GSK interactive voice response system (IVRS) by the investigator or authorized site staff. All enrolled subjects will receive GSK2849330.

3.7.2. Dosage and Administration of Study Treatment(s)

GSK2849330 will be given by IV infusion over a 1-hour period. If an infusion-related reaction occurs during administration, the infusion rate may be reduced or halted at the discretion of the investigator and/or GSK medical monitor, depending on the severity of the symptoms; the subject will receive appropriate medical treatment. When the subject's condition is stable, the infusion may be restarted according to the judgment of the investigator. Upon restart, the infusion rate should be half of the infusion rate at the time the infusion was paused.

Guidance for the monitoring and managing of infusion related reactions and allergic/hypersensitivity reactions, including anaphylaxis, are outlined in Section 3.9.1 and Section 3.9.2.

Subjects should be monitored for at least 1 hour after the completion of the infusion and may be discharged if considered clinically stable and all other study procedures have been completed.

Guidelines for dosage modifications are provided in Section 3.9.4.

The dose of study treatment is discussed in Section 3.3 and Section 3.4.

3.7.3. Blinding

This is an open-label study.

3.8. Safety Management Guidelines

3.8.1. Liver Chemistry Stopping Criteria

Liver chemistry threshold stopping criteria have been designed to assure subject safety and to evaluate liver event etiology during administration of study treatment(s) and the follow-up period. Study treatment(s) will be stopped if any of the following liver chemistry stopping criteria is/are met:

1. ALT ≥ 3 times ULN and bilirubin ≥ 2 times ULN (or ALT ≥ 3 times ULN and international normalization ratio [INR] > 1.5)

NOTE: Serum bilirubin fractionation should be performed if testing is available. If fractionation is unavailable, urinary bilirubin is to be measured via dipstick (a measurement of direct bilirubin, which would suggest liver injury).

2. ALT ≥ 5 times ULN.
3. ALT ≥ 3 times ULN if associated with the appearance or worsening of rash or hepatitis symptoms (fatigue, nausea, vomiting, right upper quadrant pain, tenderness or jaundice) or hypersensitivity (such as fever, rash or eosinophilia, other than that as described in Section 3.9.1 and Section 3.9.2).

4. ALT ≥ 3 times ULN persists for ≥ 4 weeks.
5. ALT ≥ 3 times ULN and cannot be monitored weekly for 4 weeks.

Subjects with ALT ≥ 3 times ULN **and** < 5 times ULN **and** bilirubin < 2 times ULN, who do not exhibit hepatitis symptoms or rash, can continue study treatment(s) as long as they can be monitored weekly for 4 weeks. See following section for details on weekly follow-up procedures for these subjects.

3.8.1.1. Liver Chemistry Follow-up Procedures

Refer to the diagram in [Appendix 1](#) for a visual presentation of the procedures listed below.

The procedures listed below are to be followed if a subject meets the liver chemistry stopping criteria defined in Section [3.8.1](#).

- Immediately and permanently withdraw the subject from study treatment.
- Notify the GSK Medical Monitor within 24 hours of learning of the abnormality to confirm the subject's study treatment(s) cessation and follow-up.
- Complete the "Safety Follow-Up Procedures" listed below.
- Complete the liver event electronic case report forms (eCRFs). If the event also meets the criteria of a SAE (see Section [8.2](#)), the SAE data collection tool will be completed separately with the relevant details.
- Upon completion of the safety follow-up permanently withdraw the subject from the study and do not rechallenge with study treatment(s).

Safety Follow-Up Procedures for subjects with ALT ≥ 3 times ULN:

- Monitor subjects **weekly** until liver chemistries (ALT, aspartate aminotransferase [AST], alkaline phosphatase [ALP], and bilirubin) resolve, stabilize or return to within baseline values.

Safety Follow-Up Procedures for subjects with ALT ≥ 3 times ULN and bilirubin ≥ 2 times ULN (or ALT ≥ 3 times ULN and INR > 1.5):

- **This event is considered an SAE** (see Section [8.2](#)). Serum bilirubin fractionation should be performed if testing is available. If fractionation is unavailable, urinary bilirubin is to be measured via dipstick (a measurement of direct bilirubin, which would suggest liver injury).
- Make every reasonable attempt to have subjects return to the clinic within 24 hours for repeat liver chemistries, additional testing, and close monitoring (with specialist or hepatology consultation recommended).
- Monitor subjects **twice weekly** until liver chemistries (ALT, AST, alkaline phosphatase, bilirubin) resolve, stabilize or return to within baseline values.

In addition, for all subjects with ALT ≥ 3 times ULN, every attempt must be made to also obtain the following:

- Viral hepatitis serology including:
 - Hepatitis A Immunoglobulin M (IgM) antibody.
 - Hepatitis B surface antigen and hepatitis B core antibody (IgM).
 - Hepatitis C RNA.
 - Cytomegalovirus IgM antibody.
 - Epstein-Barr viral capsid antigen IgM antibody (or if unavailable, obtain heterophile antibody or monospot testing).
 - Hepatitis E IgM antibody (if subject resides outside the United States (US) or Canada, or has traveled outside US or Canada in past 3 months).
- Blood sample for PK analysis, obtained within 30 days of last dose. Record the date/time of the PK blood sample draw and the date/time of the last dose of study treatment(s) prior to blood sample draw on the eCRF. If the date or time of the last dose is unclear, provide the subject's best approximation. If the date/time of the last dose cannot be approximated OR a PK sample cannot be collected in the time period indicated above, **do not obtain a PK sample**. Instructions for sample handling and shipping are included in the SPM.
- Serum creatine phosphokinase and lactate dehydrogenase.
- Fractionate bilirubin, if total bilirubin ≥ 2 times ULN.
- Obtain complete blood count with differential to assess eosinophilia
- Record the appearance or worsening of clinical symptoms of hepatitis or hypersensitivity (other than as described in Section 3.9.1 and Section 3.9.2) such as fatigue, nausea, vomiting, right upper quadrant pain or tenderness, fever, rash or eosinophilia, on the AE eCRF.
- Record use of concomitant medication(s), acetaminophen, herbal remedies, other over-the-counter medication(s), or putative hepatotoxins on the Concomitant Medications eCRF.
- Record alcohol use on the Liver Events eCRF.

The following are required for subjects with ALT ≥ 3 times ULN **and** bilirubin ≥ 2 times ULN but are optional for other abnormal liver chemistries:

- Anti-nuclear antibody, anti-smooth muscle antibody, and Type 1 anti-liver kidney microsomal antibodies.
- Liver imaging (ultrasound, magnetic resonance imaging [MRI] or computed tomography [CT] scan) to evaluate liver disease.
- Liver Imaging and/or Liver Biopsy eCRFs are also to be completed if these tests are performed.

- Serum acetaminophen adduct high-performance liquid chromatography (HPLC) assay (quantifies potential acetaminophen contribution to liver injury in subjects with definite or likely acetaminophen use in the preceding week [James, 2009]).

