6.3. Permanent Discontinuation from Study Treatment

Subjects will receive study treatment until disease progression, death or unacceptable toxicity, including meeting stopping criteria for liver chemistry defined in Section 3.8.1. In addition, study treatment may be permanently discontinued for any of the following reasons:

- major deviations(s) from the protocol
- request of the subject or proxy (withdrawal of consent by subject or proxy)
- investigator's discretion
- a dose delay for toxicity of > 2 weeks unless the investigator or GSK Medical Monitor agree that further treatment may benefit the subject
- intercurrent illness that prevents further administration of study treatment
- subject is lost to follow-up, or the study is closed or terminated.

The primary reason study treatment was permanently discontinued must be documented in the subject's medical records and eCRF.

If the subject voluntarily discontinues from treatment due to toxicity, 'AE' will be recorded as the primary reason for permanent discontinuation on the eCRF.

Once a subject has permanently discontinued from study treatment, the subject will not be allowed to be retreated.

All subjects who discontinue from study treatment will have safety assessments at the time of discontinuation and during post-study treatment follow-up as specified in Time and Events Tables (see Section 7.1).

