9. LIVER CHEMISTRY FOLLOW-UP PROCEDURES

9.1. Liver Chemistry Testing Procedures

For subjects meeting any of the liver chemistry stopping criteria in Section 3.8.1, make every attempt to carry out the **liver event follow-up assessments** described below:

- Viral hepatitis serology, including:
 - Hepatitis A IgM antibody
 - Hepatitis B surface antigen and hepatitis B core antibody (IgM)
 - Hepatitis C RNA
 - Cytomegalovirus IgM antibody
 - Epstein-Barr viral capsid antigen IgM antibody (or if unavailable, then obtain heterophile antibody or monospot testing)
- Blood sample for PK analysis, obtained within 10 days of the last dose of study drug(s). Record the date and time of the PK blood sample draw and the date and time of the last dose of study drug(s) prior the blood sample draw on the eCRF. If the date or time of the last dose is unclear, provide the subject's best approximation. If the date or time of the last dose cannot be approximated, or if a PK sample cannot be collected within the 10-day period following the last dose, do not obtain a PK sample. Instructions for sample handling and shipping are found in the SPM.
- Serum creatinine phosphokinase (CPK) and lactate dehydrogenase (LDH).

- Fractionate bilirubin, if total bilirubin ≥ 2 X ULN.
- Obtain a complete blood count (CBC) with differential to assess eosinophilia.
- Record the appearance or worsening of clinical symptoms indicative of hepatitis or hypersensitivity, such as fatigue, nausea, vomiting, right upper quadrant pain or tenderness, fever, rash or eosinophilia as relevant on the AE eCRF.
- Record the use of concomitant medications, including acetaminophen, herbal remedies or any other over the counter (OTC) medications, or any putative hepatotoxins, on the concomitant medication eCRF.
- Record alcohol use on the liver event alcohol intake eCRF.

The following assessments are required for subjects with ALT ≥ 3 X ULN and bilirubin ≥ 2 X ULN (>35% direct) but are optional for other abnormal liver chemistries:

- Anti-nuclear antibody, anti-smooth muscle antibody, and Type 1 anti-liver kidney microsomal antibodies.
- Liver imaging (ultrasound, MRI or CT) to evaluate liver disease.

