9.3. Drug Restart/Rechallenge Following Liver Events that are Possibly Related to Study Drug(s)

Approval by the GSK Medical Monitor to restart/rechallenge study drug(s) may be considered where:

- The subject is receiving compelling benefit, the benefit exceeds the risk, and no effective alternative therapy is available. Approval of restart/rechallenge by the IRB or Independent Ethics Committee (IEC) must be obtained, as required.

- If the restart/rechallenge is approved by GSK in writing, then the subject must be provided with a clear description of the possible benefits and risks of administration of study drug(s), including the possibility of a recurrence, a more severe liver injury or death.
- The subject must also provide signed informed consent specifically for the study drug(s) restart/rechallenge. Documentation of the informed consent must be recorded in the subject's study chart.
- Study drug(s) must be administered at the dose specified by the GSK Medical Monitor.
- Subjects approved by GSK for restart/rechallenge of study drug(s) must return to the clinic twice a week for evaluation of liver chemistry tests until stable liver chemistries have been demonstrated and laboratory monitoring may resume per protocol.

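### After the liver stopping criteria, Protocol 3.8.1.1 and 6.3 bar restart while 9.3 and 9.4 allow it on approval, with no cross-reference; the liver-event PK sample also has two windows, 30 and 10 days

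*Protocol*

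**What the plan says.** **Restart barred.** Protocol Section 3.8.1.1 sets its own scope: "The procedures listed below are to be followed if a subject meets the liver chemistry stopping criteria defined in Section" 3.8.1. Its first instruction is: "Immediately and permanently withdraw the subject from study treatment". Its last, once safety follow-up is complete, is to "permanently withdraw the subject from the study and do not rechallenge with study treatment(s". Section 6.3 says treatment runs until, among other events, "unacceptable toxicity, including meeting stopping criteria for liver chemistry defined in Section 3.8.1". It then adds a general rule: "Once a subject has permanently discontinued from study treatment, the subject will not be allowed to be retreated".

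**Restart allowed.** Section 9.3 concerns liver events possibly related to study drug: "Approval by the GSK Medical Monitor to restart/rechallenge study drug(s) may be considered where" its conditions are met. It asks for a strong individual benefit with no effective alternative, ethics approval as required, written sponsor approval, consent specific to the restart, a dose set by the Medical Monitor, and twice-weekly liver tests. Section 9.4 offers a similar route after transient events not related to study drug, with weekly tests.

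**PK sample.** Section 3.8.1.1 lists: "Blood sample for PK analysis, obtained within 30 days of last dose". Section 9.1 lists: "Blood sample for PK analysis, obtained within 10 days of the last dose of study drug(s". Each adds that the sample should not be taken if its own window cannot be met.

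The SAP has no rule on liver rechallenge or on the liver-event PK window.

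**The concern.** A prohibition without exception and a procedure for approving the prohibited act sit in the same protocol, and neither refers to the other. If restart is raised for a subject stopped under 3.8.1, the answer depends on which section is opened. Section 9.3 itself requires the subject to be told that restart could bring recurrence, worse liver injury or death, so whether re-exposure is possible at all should not be left unclear. Section 3.1 excludes waivers, so the conflict cannot properly be settled case by case.

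The PK conflict is smaller. It concerns the sample meant to show drug exposure around a liver event. Two sites acting in good faith could differ on whether to draw it, and liver-event exposure data would then be collected unevenly.

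**Working it through.** The plan gives no figure to reproduce, so this is a comparison of the current protocol text. The amendment log was left out because it records superseded wording.

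**1. Do the sections concern the same subjects?**
- 3.8.1.1 applies to subjects who meet the 3.8.1 criteria, and 6.3 names those criteria as ending treatment.
- 9.1 opens with subjects who meet any 3.8.1 criterion.
- 9.2 covers milder ALT elevations without symptoms. Those subjects stay on drug, so they have nothing to restart. If one later meets any of criteria 1 to 5, 9.2 directs the site to Section 9.
- 8.5.2 instead sends the reader to 3.8.1 for stopping criteria and follow-up.
- 9.3 and 9.4 state no entry criterion of their own. Nothing in them excludes subjects stopped under 3.8.1.

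The cross-references therefore lead the same subject to both sets of rules.

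**2. Is an exception written anywhere?** Neither 3.8.1.1 nor 6.3 mentions 9.3 or 9.4. Sections 9.3 and 9.4 do not mention 3.8.1.1 or 6.3.

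**3. When do the restart rules collide?**
- Restart never considered: every section is satisfied, because 9.3 and 9.4 only permit.
- Restart considered and the 9.3 or 9.4 conditions met: 3.8.1.1 and 6.3 refuse what 9.3 or 9.4 allows to be approved.

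**4. When do the PK windows collide?** All five 3.8.1 criteria need ALT of at least 3 times ULN (criterion 2 needs 5 times). The 3.8.1.1 sample list covers all subjects at or above 3 times ULN, so every subject under 9.1 is also under that list.

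| Days since last dose | 3.8.1.1 | 9.1 |
|---|---|---|
| Up to 10 | seek sample | seek sample |
| 11 to 30 | seek sample | do not take it |
| After 30 | do not take it | do not take it |

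The windows differ by 30 − 10 = 20 days.

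**5. Can days 11 to 30 arise in routine conduct?** In the continuation phase of Tables 7, 8 and 11, chemistry and infusion share the same interval. The dosing window is ±2 days for weekly dosing and ±3 days otherwise. Suppose an abnormal result is known before that day's infusion and no earlier dose was missed or further delayed. The last dose was then:
- weekly: 7 ± 2 = 5 to 9 days earlier, inside both windows;
- every 2 weeks: 14 ± 3 = 11 to 17 days earlier, wholly in the conflict range;
- every 3 weeks: 21 ± 3 = 18 to 24 days earlier, wholly in the conflict range.

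This shows that the situation is ordinary on two of the three schedules. It does not estimate how often it would occur.

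**The case against.** **Every section can be obeyed at once.** A reader might infer that compliance with both sets of rules is impossible. It is not: never restarting, and sampling by day 10, satisfies all of them. Nor is the 30-day sample strictly mandatory; both sections ask for every effort to obtain it. This stands and limits the point, but it does not remove the conflict once restart is considered or once day 10 has passed.

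**Restart is controlled centrally.** A reader might also infer that sites could handle the same event in opposite ways on their own authority. The documents do not support that for restart. The Medical Monitor must be told of a stopping event within 24 hours, and restart needs Medical Monitor approval, written sponsor approval and specific consent. What remains is that the sponsor's own staff have no single rule to apply.

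**9.3 and 9.4 may have another use.** They do not say that they follow the 3.8.1 criteria. Section 3.9.4 also stops or delays treatment for other toxicity judged clinically significant. That could include an isolated bilirubin, AST or alkaline phosphatase rise that meets no 3.8.1 criterion. Restart after such a hold would contradict neither 3.8.1.1 nor 6.3. This use is possible, but neither section is limited to it, and an exception to an unqualified ban should be written down.

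**Appendix 1 could not be checked.** Its liver algorithm is a figure that was not available. If it states an exception, the text would still disagree with it.

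**Consequences for the data are limited.** Section 7.4 schedules PK at the Follow-up visit, about 28 days after the last dose, and/or at the Post-study visit, so later exposure data are not necessarily lost. The SAP's liver-event summary tables use each subject's first event. A restart would not change that count, so a claim that interpretation of liver events is distorted goes beyond the documents.

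**Conclusion.** The inconsistency is real and lies in the current protocol text. For subjects stopped under 3.8.1, restart is barred without exception in 3.8.1.1 and 6.3 and open to approval in 9.3 and 9.4. The liver-event PK sample has two windows that disagree on days 11 to 30.

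Its reach should not be overstated. Meeting any of the five criteria makes a subject stop, and all sections agree on that. The restart conflict touches only those for whom restart is then considered, and the documents give no basis for estimating how many that is. The 20-day difference is a span of calendar time, not a frequency.

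The conclusion assumes that 9.3 and 9.4 include subjects stopped under 3.8.1, which follows from the links in 9.1 and 9.2 and from the absence of any stated limit. This is a matter of patient safety and consistent conduct. Sample size, power and error rates are unaffected.

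**What to change.** - Reconcile Sections 3.8.1.1, 6.3, 9.3 and 9.4 so that one restart rule applies to subjects who meet the 3.8.1 criteria. State which subjects 9.3 and 9.4 cover, and write any exception, with a cross-reference, in each of the four sections.
- Reconcile Sections 3.8.1.1 and 9.1 to one PK sampling window after a liver event.
- Check that the Appendix 1 diagram agrees with the result.

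Which restart rule and which window are right is for the sponsor to decide; this review proposes neither. The cost is protocol wording at the next amendment. No change to the design or the SAP analyses is needed.
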